### **3.8.2.8 Failure-free-survival (FFS)**

FFS is defined as the absence of new cGVHD systemic therapy, non-relapse mortality and recurrent malignancy (i.e. underlying disease) and is censored by last response assessment or long term follow up assessment, whichever is the latest and available. Kaplan-Meier plots, descriptive statistics of FFS and landmark FFS at 6, 12, 18 and 24 months will be provided. In addition, analyses for the three components of FFS will also be provided.

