*** These items must be completed on Day 1 of Cycles 2, 3, 5, 7, then on Day 1 of every 3 cycles thereafter, (Day 1 of Cycles 10, 13, 16, 19, etc.). These items may be completed on Day 1 of other cycles if deemed appropriate by the Investigator.**

Note: On Day 1 of Cycles 8 and beyond, participants will come to the clinic to have the same procedures as described above, except belumosudil may be administered at home or in the clinic (procedures can then be pre- or post-dose).

On Cycle 2 Day 1 (C2D1) participants will receive study drug for 1 cycle along with 1 diary. On Cycle 3 and 5 Day 1 (C3D1 and C5D1), participants will receive the study drug for the next 2 cycles along with 2 diaries, and from cycle 7 onwards (C7D1, C10D1, C13D1, etc.) participants will receive the study drug for 3 cycles along with 3 diaries and return to the clinic every 3 cycles for assessments and investigational product accountability. On cycles when participants do not come to clinic, the study staff will contact the participant, eg, via phone and document any new AEs and concomitant medications. Also, from C19D1 onwards, ECGs will be done only if clinically indicated.

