6.2.5 End of Treatment (EOT)

Participants are to return to the study site within 7 days after the participant's last dose of study drug to complete all EOT assessments. This may occur at the visit at which disease progression is diagnosed. The following procedures will be completed:

- Concomitant medications assessment.
- AE assessment.
- Symptom directed PE.

- Highly sensitive urine or serum pregnancy test (for females of childbearing potential). Positive results are to be confirmed with serum testing.
- Weight measurement.
- Height and BMI if aged <18 years.
- Seated vital sign measurements (sitting blood pressure, pulse, respiratory rate, temperature).
- Karnofsky (if aged \geq 16 years) / Lansky (if aged <16 years) Performance Scale score ([Appendix G](#)).
- Hematology ([Table 4](#)).
- Clinical Chemistry ([Table 4](#)).
- Single 12-lead ECG ([Table 10](#)).
- Full PFTs (including FEV₁, FVC, DLCO (corrected for Hb), TLC, and RV) or spirometry (FEV₁, FVC) if full PFTs have been taken in the previous month.
- Clinician-Reported Global cGVHD Activity Assessment.
- Response assessment.
- Pharmacodynamic sampling in event of progression of cGVHD.
- cGVHD Activity Assessment - Patient Self Report.
- Lee cGVHD Symptom Scale.
- PROMIS Global Health score ([Appendix E](#)).
- Document corticosteroid dosage.
- Document other cGVHD therapies.
- Collect study drug.
- Collect study drug diary.

If the participant is discontinuing study due to enrolling in the KD025-217 study, the EOT visit is expected to be the same day as C1D1 of KD025-217. The EOT visit for these participants rolling into the extension study includes minimal assessments: collect study drug and collect study drug diary.

If the participant is discontinuing and not participating in KD025-217, all the EOT visit assessments are to be performed.

6.2.6 28-Day Follow-Up Visit

The follow-up visit should occur 28 (± 7) days after the last dose of study drug. However, when possible, this visit should occur prior to starting on a new cGVHD therapy (if a new therapy is started earlier). Participants will return to the clinic and the following procedures will be completed:

- Concomitant medications assessment.
- AE assessment.
- Symptom directed PE.
- Highly sensitive urine or serum pregnancy test (for females of childbearing potential). Positive urine results are to be confirmed with serum testing.
- Weight measurement.

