### **3.8.2.5 Time to Next Therapy (TTNT)**

The TTNT will be measured as the time from first treatment to the time of new systemic cGVHD treatment, censored by last response assessment or long term follow up assessment, whichever is the latest and available. TTNT will be analyzed by the Kaplan-Meier survival method as well as the landmark analysis at 6, 12, 18, and 24 months.

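### FFS and TTNT censor event-free participants at the last assessment or call but still count later events, which biases both curves modestly downward.

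*SAP*

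**What the plan says.** SAP 3.8.2.8: "FFS is defined as the absence of new cGVHD systemic therapy, non-relapse mortality and recurrent malignancy". A participant without such an event "is censored by last response assessment or long term follow up assessment, whichever is the latest and available". Landmarks follow: "landmark FFS at 6, 12, 18 and 24 months will be provided".

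SAP 3.8.2.5 defines the endpoint first: "The TTNT will be measured as the time from first treatment to the time of new systemic cGVHD treatment". Death is not a TTNT event. For a participant who has not started such therapy, the section then says the time is "censored by last response assessment or long term follow up assessment, whichever is the latest and available". It also plans a "landmark analysis at 6, 12, 18, and 24 months".

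Event dates are treated differently from censoring dates. SAP 3.14 (missing event dates) imputes a date only where the day is missing, so any other event keeps its recorded date. The DOR censoring table in SAP 3.8.2.1 moves an event back when it follows two or more missed assessments; FFS and TTNT have no such provision. The SAP states no data cut-off that ties events to the contact used for censoring.

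The data are collected as follows:
- Response (Protocol 3.1): every 4 weeks up to Day 1 of Cycle 5, then every 8 weeks; wider spacing for adolescents enrolled after Amendment 5.
- Long-term follow-up (Protocol 6.2.8): contact about every 12 weeks.
- Other cGVHD therapies and adverse events (Protocol 21.1, Table 6): collected from consent to 28 days after the last dose, not only at response visits.
- Cycles without a clinic visit (Protocol 6.2.4): "the study staff will contact the participant, eg, via phone and document any new AEs and concomitant medications".
- End-of-treatment visit for participants entering the rollover study (Protocol 6.2.5): "includes minimal assessments: collect study drug and collect study drug diary", so no response assessment.

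**The concern.** A Kaplan-Meier estimate needs events and event-free time to be observed over the same window. Here the window depends on the outcome. Take two participants last assessed on the same day. One starts new systemic therapy five weeks later and counts as an event at week five. The other is still event-free at week five but is censored at the assessment. The first adds an event to the recent risk set; the second, who should be in its denominator, has left it.

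The hazard is therefore overstated in the last weeks of each participant's follow-up. The effect builds up at landmarks where many participants are close to the end of their follow-up. FFS comes out too low and the need for new therapy too high. The confidence intervals do not reflect this.

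These are single-arm style estimates, reported by dose and read on their own, so a systematic shift is not cancelled by a comparison with a control.

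**Working it through.** The documents give no FFS or TTNT rate, hazard or event count, so there is no stated figure to reproduce. The size of the bias has to come from assumptions.

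**Inputs from the documents.** N = 126. Primary analysis about 6 months, and follow-up analysis about 12 months, after the 126th treated participant (SAP 3). Enrolment about 24 months (Protocol 3.3). Response and call schedule as above.

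**Assumptions.** Uniform accrual. Exponential time to event, median 12 months (9 and 18 also run), so λ = ln 2 / 12 = 0.0578 per month. Median 18 months to stopping drug without an event. Accrual over 12 months run as an alternative.

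**Step 1: simulation.** The SAP rule was compared with censoring event-free participants at the data cut, 800 trials per setting. For median 12 months:

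| Setting | 6 mo | 12 mo | 18 mo | 24 mo |
|---|---|---|---|---|
| True FFS, % | 70.7 | 50.0 | 35.4 | 25.0 |
| Primary analysis, 24-month accrual: SAP rule, % | 70.6 | 48.8 | 33.7 | 22.7 |
| Difference from cut-off censoring, points | -0.1 | -1.0 | -1.7 | -2.4 |
| Mean number at risk | 84 | 44 | 21 | 6 |
| Follow-up analysis, 24-month accrual: SAP rule, % | 70.7 | 49.8 | 34.6 | 23.8 |
| Difference from cut-off censoring, points | 0 | -0.1 | -0.7 | -1.2 |
| Mean number at risk | 89 | 60 | 32 | 14 |

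A repeat simulation gave biases of 1.2, 1.9 and 2.6 points (primary) and 0.1, 0.8 and 1.3 points (follow-up) at 12, 18 and 24 months. Over medians of 9 to 18 months with 24-month accrual, the 24-month bias is 2.0 to 2.6 points (primary) and 1.0 to 1.4 points (follow-up). With 12-month accrual at the primary analysis, the 12-month bias is 2.3 to 2.7 points.

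**Step 2: hand check of the mechanism.** The mean gap from censoring date to data cut is 35 days (1.15 months) at the primary analysis and 37 days (1.22 months) at the follow-up analysis, with 24-month accrual. With follow-up uniform from f to f + 24 months, the expected number event-free at the cut is

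126 × (e^(-λf) - e^(-λ(f+24))) / (24λ).

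- Primary, f = 6: 126 × (0.7071 - 0.1768) / 1.3863 = 48.2. Events in the gap: 48.2 × (e^(0.0578 × 1.15) - 1) = 3.3.
- Follow-up, f = 12: 126 × (0.5000 - 0.1250) / 1.3863 = 34.1. Events in the gap: 34.1 × (e^(0.0578 × 1.22) - 1) = 2.5.

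The simulation counted 3.3 and 2.5 events after the last contact. So about three events are kept, while some 48 event-free participants lose 35 days each (48.2 × 35 / 365.25 = 4.6 person-years) at the primary analysis.

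**Step 3: how events become known.** If events after stopping drug are learned only at calls, the follow-up-analysis bias with 24-month accrual falls from 0.7 and 1.2 to 0.3 and 0.5 points at 18 and 24 months. With 12-month accrual at the primary analysis, the 12-month bias falls from 2.6 to 1.5 points.

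**Step 4: what removes it.**
- Moving only the censoring date to the last documented contact (monthly on treatment, calls afterwards) recovers 0.3, 0.4 and 0.4 of 1.0, 1.7 and 2.5 points at 12, 18 and 24 months (primary analysis, 24-month accrual).
- Counting events only up to the contact used for censoring gives zero bias at all four landmarks (follow-up analysis, 24-month accrual).

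**The case against.** The strongest reply is that the effect is small and safe. FFS and TTNT are descriptive and carry no alpha (SAP 3 and 3.2), the same rule applies to both arms, and the error works against the drug. The Kaplan-Meier standard deviation is about 4 to 5 points. The protocol itself asks only for median FFS and the 1-year landmark (Protocol 11.7.2), where the follow-up analysis is off by about 0.1 point. In long-term follow-up the call is where status is confirmed, so censoring there is appropriate. All of this stands and limits the grade of the point. It does not make the rule right: the SAP adds 18- and 24-month landmarks, and the shift is avoidable.

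A second reply is that new systemic therapy requires stopping drug (Protocol 5.8), which brings an end-of-treatment visit with a response assessment. But that visit follows from the event. It helps the event to be recorded and gives event-free participants no later date.

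Some stronger readings are tempting, and the documents do not support them:
- *TTNT also counts deaths.* It does not; its only event is new systemic therapy. FFS counts non-relapse deaths, not all deaths.
- *The bias reaches 8 to 12 points at 18 months.* That needs 12-month accrual and the primary analysis, where 12 + 6 = 18 months is the longest possible follow-up and nobody remains at risk. No censoring rule makes that landmark estimable, and the current protocol plans about 24 months of enrolment.
- *Different visit spacing distorts an adult-adolescent comparison.* SAP 3.8.4 plans subgroups only for ORR and DOR and splits age at 65. No such FFS comparison is planned.
- *Rollover censoring drives the primary analysis.* Rollover came with Amendment 3 (August 2021), after the July 2021 approval that the protocol attributes to this study's data. It can matter only for later analyses.

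**Conclusion.** The point holds as a modest, avoidable downward bias in two descriptive endpoints. As written, the two SAP sections keep events after the last contact and discard event-free time over the same interval.

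The size rests on an exponential distribution with an assumed 12-month median, uniform accrual, an assumed rate of stopping drug, and events after the last contact being reported and counted. The 24-month figures also rest on few participants at risk. The reported landmark values would look slightly worse for the drug than they should, by less than their sampling error. The efficacy conclusion on ORR does not depend on this.

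**What to change.** In SAP 3.8.2.5 and 3.8.2.8, apply one rule to events and censoring:

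- For each participant, define the last date with documented event status from any source already collected: clinic visit, phone contact, therapy or concomitant-medication record, rollover visit or follow-up call. Cap it at a stated data cut-off.
- Censor event-free participants at that date.
- Count events only up to the participant's last scheduled status contact or, where status is confirmed through it, the data cut-off. A visit that takes place because of the event must not extend this window, or the asymmetry returns.
- Report the number at risk at each landmark.

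Both halves are needed, since moving the censoring date alone recovers only a small part of the bias at the primary analysis. The cost is two SAP sentences and one derived date, with no new data collection. The downside is that a few late events (about 2 to 5 in the settings run) are not counted until the next analysis.

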### **3.8.2.9 Overall survival (OS)**

OS is defined as time from first dose of KD025 to the date of death due to any cause. Kaplan-Meier plots, descriptive statistics of OS and landmark OS at 6, 12, 18 and 24 months will be provided.

### **3.8.2.10 Change in cGVHD severity using the Clinician-Reported Global cGVHD Activity Assessment**

The Clinician-reported global cGVHD Activity Assessment is a 0-10 point numeric rating scale with a score of 0 indicating “cGVHD symptoms not at all severe” and a score of 10 being “Most severe cGVHD symptoms possible”. The activities are assessed on Day 1 of each cycle from Cycle 1 Day 1 to EOT.

Change from baseline in cGVHD severity based on the Clinician-reported global cGVHD Activity Assessment will be summarized as a categorical endpoint at all scheduled assessment visits.

### **3.8.2.11 Change in symptom activity using the cGVHD Activity Assessment Patient Self-Report**

The cGVHD Activity Assessment-Patient Self Report is in Protocol Appendix F. Activities are assessed on Day 1 of each cycle from C1D1 to end of treatment (EOT). The symptom activity item is a 0-10-point numeric rating scale with a score of 0 indicating “cGVHD symptoms not at all severe” and a score of 10 being “most severe cGVHD symptoms possible”. The status reported by subjects are categorized as none, mild, moderate, and severe. The comparison of cGVHD symptoms to a month ago will also be reported by subjects, ranging from -3 (very much worse) to +3 (very much better).

Changes in cGVHD symptoms based on global cGVHD Activity Assessment by the Patient Self Report will be summarized as a continuous endpoint at all scheduled assessment visits. Both scores as well as the change-from-baseline values will be presented.

The summary of the change-from-baseline of Global Severity Rating on categorical status and the summary of comparison of cGVHD to a month ago will also be presented.

The number and percentage of subjects reporting none, mild, moderate, and severe cGVHD will be summarized by visit.

In addition to the specific analyses described above, descriptive statistics by visit and arm will be provided for all applicable secondary endpoints.

### **3.8.2.12 Additional Analyses**

Additional analyses will be presented including:

- ORR and DOR for responses occurring within the first 6 and 12 months of treatment with KD025
- Organ responses according to baseline NIH / severity score
- Landmark FFS with CR/PR at 6 months and at 12 months
- Time to corticosteroid discontinuation

### **3.8.3 Exploratory Endpoints**

#### **3.8.3.1 Changes in the PROMIS Global Health subscores for physical and mental functioning (see definition in Protocol Appendix E)**

Patient-Reported Outcomes Measurement Information System (PROMIS), a state-of-the-science PRO measurement system, was developed using mixed qualitative and quantitative methods and uses item response theory–calibrated item banks for numerous patient-reported symptoms and functional domains. These PRO measures can be used across chronic diseases and in the general population. A feature of PROMIS measures is that an individual's or group's score is represented as a T score, normalized and calibrated against the US population (United States population average score, 50; 10 points = 1 standard deviation [SD]). The PROMIS Global Health 10 measure comprises ten items with two summary scores for physical and mental functioning with higher scores indicating better functioning. Those two summary scores were calculated using the Assessment Center Scoring Service ([https://www.assessmentcenter.net/ac\\_scoringservice](https://www.assessmentcenter.net/ac_scoringservice)) from raw data.

Analyses will include:

- Both raw scores and change-from-baseline values (physical and mental domains) will be summarized as continuous variables by visit.
- Number of subjects with a  $\geq 4.7$ -point reduction from baseline (C1D1)

These analyses will be performed on mITT, responder and nonresponder populations.

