6.3.3.3 PROMIS Global Health Score

As an exploratory endpoint, changes in the PROMIS Global Health subscores for physical and mental functioning will be evaluated ([Appendix E](#)) (29).

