21.4 APPENDIX D: LEE CGVHD SYMPTOM SCORE

21.5 APPENDIX E: PROMIS GLOBAL HEALTH SCORE

	Please respond to each item by marking one box per row	Excellent	Very Good	Good	Fair	Poor
Global 01	In general, would you say your health is:	 5	 4	 3	 2	 1
Global 02	In general, would you say your quality of life is:	 5	 4	 3	 2	 1
Global 03	In general, how would you rate your physical health?	 5	 4	 3	 2	 1
Global 04	In general, how would you rate your mental health, including your mood and your ability to think?	 5	 4	 3	 2	 1
Global 05	In general, how would you rate your satisfaction with your social activities and relationships?	 5	 4	 3	 2	 1
Global 09	In general, please rate how well you carry out your usual social activities and roles. (This includes activities at home, at work and in your community, and responsibilities as a parent, child, spouse, employee, friend, etc.)	 5	 4	 3	 2	 1
		Completely	Mostly	Moderately	A Little	Not At All
Global 06	To what extent are you able to carry out your everyday physical activities such as walking, climbing stairs, carrying groceries, or moving a chair?	 5	 4	 3	 2	 1
		Never	Rarely	Sometimes	Often	Always
Global 10	How often have you been bothered by emotional problems such as feeling anxious, depressed or irritable?	 5	 4	 3	 2	 1
		None	Mild	Moderate	Severe	Very Severe
Global 08	How would you rate your fatigue on average?	 5	 4	 3	 2	 1

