**Figure 2 ORR Multiplicity Adjustment**

Simulations were conducted with various hypothetical ORR scenarios for two arms of 63 subjects, by using the Hochberg procedure for multiplicity adjustment; results (10000 runs per setting) are presented in [Table 1](#).

Only descriptive statistics will be provided for all secondary and exploratory endpoints, without multiplicity adjustment.

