### 3.8.2.2 Lee Symptom Scale Score (LSS)

Lee cGVHD Symptom Scale (see questionnaire in Protocol Appendix D) will be assessed on Day 1 of Cycles 2-5, then on Day 1 of every other Cycle thereafter and EOT. The questionnaire consists 30 items of 7 domains: skin, eyes and mouth, breathing, eating and digestion, muscles and joints, energy, and mental and emotional. Each question is scored 0, 1, 2, 3 or 4.

A domain score will be calculated for each domain by taking the mean of all items completed if more than 50% were answered and normalizing to a 0 to 100 scale. A summary score will be calculated as average of all nonmissing domain scores if more than 50% of them are nonmissing. A higher score indicated more bothersome symptoms. 7 points difference on the summary score of cGVHD symptom scale was found to be clinically meaningful.

$$\text{Raw Score} = \frac{I_1 + \dots + I_m}{m}, \quad \text{Domain Score} = (\text{Raw Score} / 4) * 100$$

$$\text{Summary Score} = \frac{\text{Domain Score}_1 + \dots + \text{Domain Score}_n}{n}$$

In the above formulas, m is the number of items have nonmissing value in a domain, and n is the number of domains have nonmissing domain scores.

Analyses will include:

- Both score and change-from-baseline values (summary score and domain scores) will be summarized as continuous variables by visit
- Number and percent of subjects with a  $\geq 7$ -point reduction (7-PtR) from baseline (C1D1)
- Number and percent of subjects with a 7-PtR from baseline on 2 consecutive assessments
- Duration of a 7-PtR (DO7-PtR) (defined as time from documentation of the first  $\geq 7$ -point reduction to the first documentation of less than 7-point reduction). If there are multiple episodes, then DO7-PtR will be measured as the sum of DO7-PtR from all episodes.

These analyses will be performed on mITT, responder and nonresponder populations. 7-PtR and DO7-PtR will be censored after new systemic cGVHD treatment.

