F	Kaplan-Meier plot of DOR (KARA)	Responder
T	Best response by individual organ (KARA)	miITT
T	Descriptive statistics of change from baseline in PROMIS scale by visit	miITT, Responder, Nonresponder
T	Summary table of univariate modeling	miITT

\* Repeat TLF for subgroups of:

- Prior ibrutinib (Yes / No)
- Severe cGVHD at baseline (Yes / No)
- Number of organs involved at baseline (<4 / ≥4)
- Number of prior lines of therapy (≤3 / >3)
- Duration of cGVHD before enrollment (by 50th percentile)
- Baseline corticosteroid dose level (by 50th percentile)
- Lung involvement at baseline (Yes / No)
- Proton pump inhibitor (PPI) on C1D1 (Yes/No)
- Gender
- Age (<65 / ≥65 years )
- Race
- Prior ruxolitinib (Yes / No)
- Best response to the last prior treatment (SD/PD)
- Take concomitant medication proton pump inhibitor (PPI) on C1D1 (Yes/No)
- Baseline GFR (<60, 60-90 and ≥90 mL/min)

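### The only PROMIS threshold analysis counts a fall of at least 4.7 points on a scale where higher is better, so as written it counts only participants who worsened

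*SAP*

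**What the plan says.** SAP section 3.8.3.1 describes the PROMIS Global Health measure as giving "two summary scores for physical and mental functioning with higher scores indicating better functioning". Scores are T scores, with a US population mean of 50 and 10 points to one standard deviation.

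The section lists two analyses, each run in the mITT, responder and nonresponder populations:

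- raw scores and change from baseline for both domains, summarized as continuous variables by visit;
- the number of subjects with a ≥4.7-"point reduction from baseline (C1D1").

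The second is the only PROMIS threshold in either document. It does not say whether it measures improvement or worsening, or whether it applies to the physical score, the mental score or either.

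Other places that bear on the point:

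- Protocol Appendix E gives the items. For those answered on a 5-to-1 scale, such as "In general, would you say your quality of life is", the best answer is coded 5 and the worst 1.
- Protocol section 6.3.3.3 says only: "As an exploratory endpoint, changes in the PROMIS Global Health subscores for physical and mental functioning will be evaluated".
- The SAP's list of efficacy outputs (Appendix A, Table 4) has one PROMIS entry: "Descriptive statistics of change from baseline in PROMIS scale by visit".
- SAP section 3.8.2.2, on the Lee Symptom Scale, states: "A higher score indicated more bothersome symptoms". Its threshold analysis counts reductions of at least 7 points from C1D1.

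**The concern.** A threshold count for a patient-reported outcome is normally there to show how many participants gained a given amount. Here the scale and the rule point in opposite directions: higher is better, and the rule counts falls. Followed literally, the analysis cannot show how many participants improved by 4.7 points, and it produces an unlabelled count of decline.

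Two practical risks follow.

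- **Misreading.** The same three-population layout is used for the Lee scale, where a reduction is a benefit. A reader moving from the Lee results to the PROMIS results could take a PROMIS reduction as benefit too. Any contrast between responders and nonresponders would then be read backwards.
- **Undocumented departure.** A programmer must either follow the text and count decline, or reverse the sign without any record in the SAP.

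**Working it through.** No sample size, power or alpha figure is involved, and the plan gives no PROMIS figure to reproduce. The check is one of direction, followed by an illustration of size.

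**Step 1: the two rules applied to example T scores**

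Rule as written: baseline − post-baseline ≥ 4.7. Opposite rule: post-baseline − baseline ≥ 4.7.

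| Baseline → post | Change | Functioning | Counted as written | Counted as an increase of ≥4.7 |
|---|---|---|---|---|
| 40 → 35 | −5 | worse | yes | no |
| 40 → 35.3 | −4.7 | worse | yes | no |
| 40 → 40 | 0 | unchanged | no | no |
| 40 → 44.7 | +4.7 | better | no | yes |
| 40 → 45 | +5 | better | no | yes |

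On the SAP's own scale, 4.7 points is 4.7 / 10 = 0.47 population SD. No participant can meet the written rule by improving on the subscore concerned.

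**Step 2: does another place settle the purpose?**

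The protocol plans only to evaluate changes in the subscores, and the output list names only change from baseline by visit. Neither labels the threshold count as decline, and neither contains an improvement count.

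**Step 3: comparison with the Lee rule**

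| | Lee Symptom Scale (SAP 3.8.2.2) | PROMIS (SAP 3.8.3.1) |
|---|---|---|
| Meaning of a higher score | worse | better |
| Threshold | fall of ≥7 points | fall of ≥4.7 points |
| Reference visit | C1D1 | C1D1 |
| Populations | mITT, responder, nonresponder | mITT, responder, nonresponder |
| Meaning of meeting the threshold | improvement | deterioration |

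The form is the same and the meaning is reversed.

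**Step 4: illustration of size**

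Assumptions, none of them from the documents: one change per participant, normally distributed with mean m and SD s, with s from 6 to 10, and complete data. Φ is the standard normal distribution function.

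- Improved by ≥4.7: 1 − Φ((4.7 − m)/s)
- Counted as written: Φ((−4.7 − m)/s)

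For example, with m = +2 and s = 8: improved = 1 − Φ(2.7/8) = 1 − Φ(0.3375) = 0.368; as written = Φ(−6.7/8) = Φ(−0.8375) = 0.201.

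| Mean change m | s | Improved by ≥4.7 | Counted as written |
|---|---|---|---|
| 0 | 6 | 0.217 | 0.217 |
| 0 | 8 | 0.278 | 0.278 |
| 0 | 10 | 0.319 | 0.319 |
| +1 | 6 | 0.269 | 0.171 |
| +1 | 8 | 0.322 | 0.238 |
| +1 | 10 | 0.356 | 0.284 |
| +2 | 6 | 0.326 | 0.132 |
| +2 | 8 | 0.368 | 0.201 |
| +2 | 10 | 0.394 | 0.251 |
| −2 | 6 | 0.132 | 0.326 |
| −2 | 8 | 0.201 | 0.368 |
| −2 | 10 | 0.251 | 0.394 |

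In an arm of 63, a mean change of 0 gives about 14 to 20 participants under either rule. A mean change of +2 gives about 21 to 25 improved (63 × 0.326 to 63 × 0.394) against about 8 to 16 counted as written (63 × 0.132 to 63 × 0.251).

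**The case against.** The strongest reply is that nothing here is strictly contradictory. Counting participants with a meaningful decline is a legitimate descriptive analysis. The section gives the scale direction before it counts reductions, so a careful reader can interpret the result. The carry-over from the Lee rule is inferred from similar wording. This stands as far as intent goes: a deliberate count of deterioration cannot be excluded. It does not remove the problem, because in that case the count is unlabelled and no improvement count is planned.

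Second, improvement is not lost from view. The continuous change-from-baseline summaries cover all three populations, and the Lee scale and the patient self-report also capture patient-reported benefit. This is correct and limits the impact. It does not give the number of participants who improved by the SAP's own PROMIS threshold.

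Third, the stakes are low. PROMIS is exploratory, alpha goes only to ORR, and SAP section 3.2 states: "Only descriptive statistics will be provided for all secondary and exploratory endpoints, without multiplicity adjustment". This stands in full.

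Fourth, the illustration is only that. The 10-point SD in the SAP is a population SD and not the SD of a change. The threshold line does not say whether it applies at each visit or at any visit, and a count of participants who ever met it over repeated assessments would differ. Missing data would also reduce the denominators. These limits are real. The conclusion rests on the direction check, which needs none of those assumptions.

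**Conclusion.** The point holds. On a scale that the SAP itself defines as higher is better, the only PROMIS threshold analysis counts participants who worsened by at least 4.7 points. No PROMIS threshold analysis counts those who improved. The direction follows from the SAP text alone; that the wording was carried over from the Lee rule is likely but not stated.

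The size depends on the unknown mean change. Under the assumptions above, the improvement count and the written count coincide at a mean of zero, differ by 33–39% against 13–25% at +2, and reverse at −2.

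The impact is minor: no confirmatory conclusion, sample size or multiplicity rule is affected. It is still worth correcting, because the reported number changes and could be read as its opposite.

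**What to change.** In SAP section 3.8.3.1, change the threshold analysis to the number of subjects with an increase of at least 4.7 points from C1D1, described as improvement and reported separately for the physical and mental T scores. If a count of decline is also intended, keep the reduction of at least 4.7 points beside it and label it as worsening. While the line is open, it would help to say whether the threshold applies at each visit or at any visit.

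The cost is essentially one word in the SAP and the sign of one programming condition, with no new data. Protocol section 11 still plans further analyses to include the adolescent and Companion Study participants, and the correction can be applied there. For any PROMIS threshold output already produced, labelling it as a count of worsening is sufficient to prevent misreading.
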